5.0 Evaluation During Study

1. Serum pregnancy test within 10 to 14 days prior to and again within 24 hours prior to the first dose of lenalidomide for Cycles 1, 3, 5, and 7.
2. Baseline:
 - a. Thyroid function tests (TSH and free T4)
 - b. Total cortisol level
 - c. Standard chemistries including AST, ALT, Direct and Indirect Bilirubin, Alk Phos, LDH, Albumin, BUN, serum creatinine, CBC
 - d. For multiple myeloma patients only (within 30 days of registration): SPEP and serum IFE, UPEP and urine IFE, immunoglobulins IgA, IgG, IgM, Beta 2 microglobulin, Serum free kappa and lambda light chain assay. Bone marrow aspiration and biopsy. Bone survey.

3. Before Cycle 1 (if baseline tests and/or exam are > 7 days before start of Cycle 1):
 - a. Standard chemistries including AST, ALT, Direct and Indirect Bilirubin, Alk Phos, LDH, Albumin, BUN, serum creatinine, CBC
 - b. Physical examination and toxicity assessment
 - c. Creatinine clearance. Use Cockcroft-gault formula and ideal body weight (IBW). Use adjusted body weight if >50% over IBW
4. Before Cycles 3, 5, and 7:
 - a. Standard chemistries including AST, ALT, Direct and Indirect Bilirubin, Alk Phos, LDH, Albumin, BUN, serum creatinine, CBC
 - b. Physical examination and toxicity assessment
 - c. Creatinine clearance. Use Cockcroft-gault formula and ideal body weight (IBW). Use adjusted body weight if >50% over IBW
5. Day 14 (+/- 2 days) in Cycles 1, 3, 5, and 7: CBC
6. Before Cycles 2, 4, 6, and 8:
 - a. Thyroid function tests (TSH and free T4)
 - b. Total cortisol level
 - c. Standard chemistries including AST, ALT, Direct and Indirect Bilirubin, Alk Phos, LDH, Albumin, BUN, serum creatinine, CBC
 - d. Physical examination and toxicity assessment (and GVHD assessment in allos)
 - e. Ocular exam to assess for ocular toxicity if clinically indicated.
7. At 1 (+/- 7 days), 3 (+/- 10 days), 6 (+/- 15 days) months, and (+/- 30 days) for months 12, 24, and 36 after last dose of ipilimumab and/or when clinically indicated:
 - a. Physical examination and toxicity assessment.
 - b. Assessment for toxicity (through 30 days after last dose of study drug)
 - c. Assessment for GVHD (in allogeneic patients)
 - d. Thyroid function tests (TSH and free T4)
 - e. Total cortisol level
 - f. Standard chemistries including AST, ALT, Direct and Indirect Bilirubin, Alk Phos, LDH, Albumin, BUN, serum creatinine, CBC
 - g. Bone marrow aspiration and biopsy, CT scan, PET/CT scan depending on patient's type of hematologic or lymphoid malignancy
 - h. For multiple myeloma patients only: SPEP and serum IFE, UPEP and urine IFE, immunoglobulins IgA, IgG, IgM, Beta 2 microglobulin, Serum free kappa and lambda light chain assay at each visit.
Bone marrow at 1 month follow-up and as clinically indicated.
Bone survey (+/- 30 days) for months 12, 24, and 36 after last dose of ipilimumab and/or when clinically indicated.
8. The International Working Group Response Criteria (Appendix I.) will be used.
9. We will use the International Myeloma Working Group (IMWG) uniform response criteria for multiple myeloma patients. All response categories require no known evidence of progressive or new bone lesions.

International Myeloma Working Group uniform response criteria.

All response categories require two consecutive assessments made at any time.

All response categories require no known evidence of progressive or new bone lesions.

Stringent complete response (sCR) (all of the following):

1. CR as defined.
2. Normal free light chain ratio
3. Absence of clonal cells in bone marrow by immunohistochemistry or immunofluorescence (defined by absence of abnormal k/l ratio of > 4:1 or <1:2)

Complete response (CR) (all of the following):

1. Negative immunofixation in serum and urine.
2. $\leq 5\%$ plasma cells in the bone marrow.
3. Disappearance of any soft tissue plasmacytomas.

Note: While healing of pre-existing bone lesions is not required, no new lytic lesions should appear. Further compression fracture of previously known spine lesion will not be considered as progressive disease.

Very good partial response (VGPR) (one of the following):

1. Serum and urine M protein detectable by immunofixation but not by electrophoresis.
2. 90% or greater reduction in serum M protein plus urine M protein level < 100 mg per 4h.

Partial response (PR) (all of the following):

1. Reduction by $> 50\%$ in serum monoclonal protein.
2. Reduction of urinary monoclonal protein to < 200 mg/24h or $> 90\%$.

Stable disease:

1. Not meeting criteria for CR, VGPR, PR or PD.

Progressive disease (PD) (any one or more of the following):

1. Increase of $\geq 25\%$ from baseline in:
Serum M protein (absolute increase must be ≥ 0.5 g/dL).
Urine M component (absolute increase must be ≥ 200 mg/24h). Only in patients without measurable serum and urine M protein levels.
Difference between involved and unininvolved FLC levels (absolute increase must be > 10 mg/dL).
Bone marrow plasma percentage (absolute % must be $\geq 10\%$).
2. Definite development of new bone lesions or soft tissue plasmacytomas or definite increase in the size of existing bone lesions or soft tissue plasmacytomas.
3. Development of hypercalcemia (corrected serum calcium > 11.5 mg/dL or 2.65 mol/L) that can be solely attributed to the myeloma.

Relapse from CR (any one or more of the following):

1. Reappearance of serum or urine M protein by immunofixation or electrophoresis.
2. Development $\geq 5\%$ plasma cells in the bone marrow.
3. Appearance of any other sign of progression (i.e., new plasmacytoma, lytic bone lesion or hypercalcemia).

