3.0 Eligibility

3.1 Inclusion Criteria

- a. Age \geq 18 years to \leq 80 years.
- b. Hematologic or lymphoid malignancy.
- c. Autologous patients can be included anytime within 6 months post-transplant, if they had no signs of progression and meet one of the following criteria:⁸⁻⁹
 - i. Leukemia
 - ii. Lymphoma (all types of B and T cell lymphoma)
 - iii. Multiple myeloma
- d. Allogeneic patients if:
 - i. Patients had engrafted donor cells (i.e., > 20% donor T-cell from PB/PCR); and,
 - ii. Patients NOT in CR after their allogeneic transplant, and off tacrolimus and/or mycophenolate mofetil for at least 3 to 4 weeks with no signs of GVHD; or,
 - iii. Patients had evidence of relapse after their transplant who are off tacrolimus and/or mycophenolate mofetil or other immunosuppressants for GVHD for 3 to 4 weeks with no signs of GVHD (Prednisone doses \leq 10 mg are permitted as stated previously).
- e. No active infection.
- f. ANC \geq 1.5 x 10⁹/L; platelets \geq 50 x 10⁹/L.
- g. Able to adhere to the study visit schedule and other protocol requirements.
- h. Performance status: ECOG 2 or less or Karnofsky of at least 60.
- i. Cardiac EF \geq 45% by 2D-ECHO within 3 months of study entry (or within 1 month if received chemotherapy within the past 3 months).
- j. FEV1, FVC and DLCO \geq 40% within 3 months of study entry (or within 1 month if received chemotherapy within the past 3 months).
- k. Serum creatinine \leq 1.6 mg/dL and creatinine clearance \geq 30 ml/min. Creatinine clearance will be calculated using the Cockcroft-

Gault equation: Use actual body weight if it is less than or equal to ideal body weight. Use ideal body weight if patient greater than ideal body weight, but is less than or equal to 50% over ideal body weight. Use adjusted body weight if patient is greater than 50% over ideal body weight.

- I. Liver function tests (unless related to Gilbert's disease or medications)
 - i. SGPT, SGOT less than 2x the upper limit of normal range.
 - ii. Direct Bilirubin <1.6
- m. Patient or legally authorized representative able to sign informed consent.
- n. Females of childbearing potential (FCBP)† must have a negative serum or urine pregnancy test with a sensitivity of at least 50 mIU/mL within 10 - 14 days prior to study entry.

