4.0 Treatment Plan

Eligible patients will receive lenalidomide alternating with ipilimumab for 8 cycles.

Patients who are still receiving or just finished (i.e., within 3 months) the original treatment plan will be re-consented to receive 4 additional cycles (i.e., 8 total cycles).

Lenalidomide will be given daily for 21 days (Cycle 1). One dose of ipilimumab (Cycle 2) will be given within 1-3 days from the last day of lenalidomide, then followed by 4 weeks of rest.

Repeat lenalidomide daily for 21 days (Cycle 3) followed by one dose of ipilimumab (Cycle 4) within 1-3 days from the last dose of lenalidomide. Treatment will be repeated for a total of 8 cycles.

Creatinine Clearance (mL/min)	Cycles 1, 3, 5, 7	Cycles 2, 4, 6, 8
Greater than 60	Lenalidomide 10 mg PO daily for 21 days	Ipilimumab 3 mg/kg IV x 1 dose (given 1-3 days after lenalidomide, then followed by 4 weeks of rest)
30 to 60	Lenalidomide 5 mg PO daily for 21 days	Ipilimumab 3 mg/kg IV x 1 dose (given 1-3 days after the last dose of lenalidomide)

Creatinine clearance. Use Cockcroft-Gault formula and ideal body weight (IBW) as described above in inclusion criteria (Section 3.1)

If the starting combination of lenalidomide 10 mg/day alternating with ipilimumab 3 mg/kg results in toxicity in the first 3 of 3 patients (as defined in toxicity monitoring rule) then subsequent patients will be started at a lower combination dose of lenalidomide 5 mg/day (or 5 mg every other day for creatinine clearance of 30 to 60 ml/min) and ipilimumab 3 mg/kg.

4.1 Management of Immune-Mediated toxicity from ipilimumab:

There are no dose reductions for Ipilimumab. The only modifications to drug are to pause until improvement or stop.

Signs and Symptoms	Assessment of cause and severity	Procedure for adverse effects	Ipilimumab therapy
Gastrointestinal Colitis, diarrhea, blood in stool and/or abdominal pain	Exclude other causes (disease progression, GVHD, infection) Measure AE severity using NCI-CTCAE v3.0 (diarrhea/colitis severity grading scale 3)	Mild (grade 1,2): - Symptomatic therapy	Continue therapy
		Mild (grade 2) with longer term symptoms (5-7 days): - Corticosteroid therapy with prednisone 1 mg/kg/day (or equivalent)	Pause therapy until improvement to ≤ grade 1 STOP
		Symptom improvement: taper drug over 4 weeks	
		Severe (grade 3,4) or no improvement after 5 days on steroid (grade 2) or relapse after steroid taper: - Methylprednisolone 2 mg/kg/day IV	
		Symptom improvement: taper drug over 4 weeks	

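### The pre-cycle creatinine clearance rule in Section 5.0 drops the actual-weight branch of Section 3.1(k), so a patient below ideal weight with clearance near 60 mL/min can be given lenalidomide 10 mg instead of 5 mg

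*Combined protocol and SAP*

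**What the plan says.** Three places in the combined protocol and SAP state which weight enters the Cockcroft-Gault formula.

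- **Section 3.1(k), eligibility:** three branches. The first reads "Use actual body weight if it is less than or equal to ideal body weight". The second assigns the ideal weight to anyone heavier than that, as far as 50% over, and the third assigns the adjusted weight to anyone heavier still.
- **Section 4.0, note under the dose table:** "Use Cockcroft-Gault formula and ideal body weight (IBW) as described above in inclusion criteria (Section 3.1".
- **Section 5.0, items 3c and 4c:** "Use Cockcroft-gault formula and ideal body weight (IBW). Use adjusted body weight if >50% over IBW". Item 4c applies before Cycles 3, 5 and 7 without condition. Item 3c applies only in the case "Before Cycle 1 (if baseline tests and/or exam are > 7 days before start of Cycle 1". Neither item refers to Section 3.1 or Section 4.0.

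The Section 4.0 table turns the clearance into a dose for Cycles 1, 3, 5 and 7. Above 60 mL/min the dose is 10 mg daily for 21 days. At 30 to 60 mL/min it is "Lenalidomide 5 mg PO daily for 21 days". If the first three of three patients have toxicity, later patients start at 5 mg daily, or "5 mg every other day for creatinine clearance of 30 to 60 ml/min".

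**The concern.** Section 5.0 restates two of the three branches, including the adjusted-weight one, so it reads as a complete rule and not as shorthand for Section 3.1(k). Staff working from the visit schedule would use ideal weight for a patient who weighs less than ideal, whereas Section 3.1(k) calls for actual weight. The calculation is done at the point where the dose row is chosen. The discrepancy can act in one direction only, towards higher clearance and a higher dose, in a pilot study whose primary objective is safety. The fallback level uses the same 30 to 60 mL/min band, so the conflict would carry over if the starting dose were lowered.

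**Working it through.** The plan gives no figure of its own to reproduce here. The check compares the two weight rules and follows the difference through to the dose table.

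**Inputs from the documents.** The weight rules are in Sections 3.1(k) and 5.0 (3c, 4c). The dose cut at 60 mL/min, with 10 mg and 5 mg daily for 21 days, is in Section 4.0. The renal eligibility limits, creatinine at most 1.6 mg/dL and clearance at least 30 mL/min, are in Section 3.1(k).

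**Assumed inputs.** The documents give no patient data and no ideal-weight formula, so age, weight, ideal weight and creatinine in the examples are assumptions. The ratio and the windows below do not depend on them.

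**Step 1: where the rules differ.** Above ideal weight, both use ideal weight up to 50% over and adjusted weight beyond that. At exactly ideal weight, actual and ideal coincide. They differ only below ideal weight, where 3.1(k) uses actual weight and 5.0 uses ideal weight.

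**Step 2: direction and size.** For a man, Cockcroft-Gault is

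CrCl = (140 − age) × weight / (72 × creatinine),

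multiplied by 0.85 for a woman. Everything except weight cancels, so

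CrCl(5.0) / CrCl(3.1k) = ideal weight / actual weight,

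which exceeds 1 whenever actual weight is below ideal.

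**Step 3: when the dose row changes.** The row changes when CrCl(3.1k) ≤ 60 and CrCl(3.1k) × ideal/actual > 60, that is, when

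60 × (actual/ideal) < CrCl(3.1k) ≤ 60.

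| Actual / ideal weight | Clearance inflated by | 3.1(k) clearance at which the row changes (mL/min) |
|---|---|---|
| 0.95 | 5.3% | above 57.0, up to 60 |
| 0.90 | 11.1% | above 54.0, up to 60 |
| 0.85 | 17.6% | above 51.0, up to 60 |
| 0.80 | 25.0% | above 48.0, up to 60 |

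**Step 4: assumed examples.**

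- *Man, 65 years, 60 kg, ideal weight 70.5 kg (85%), creatinine 1.1 mg/dL.* The denominator is 72 × 1.1 = 79.2. Under 3.1(k): 75 × 60 / 79.2 = 56.8 mL/min, the 5 mg row. Under 5.0: 75 × 70.5 / 79.2 = 66.8 mL/min, the 10 mg row. Per course this is 21 × 5 = 105 mg against 21 × 10 = 210 mg. He meets the renal limits of 3.1(k).
- *Woman, 60 years, 50 kg, ideal weight 56.9 kg (88%), creatinine 0.8 mg/dL.* Under 3.1(k): 0.85 × 80 × 50 / 57.6 = 59.0 mL/min, 5 mg. Under 5.0: 0.85 × 80 × 56.9 / 57.6 = 67.2 mL/min, 10 mg.
- *The same man at 68 kg (96% of ideal).* Under 3.1(k): 75 × 68 / 79.2 = 64.4 mL/min. Under 5.0: 66.8 mL/min. Both give the 10 mg row, so being below ideal weight does not by itself change the dose.

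**Step 5: a case during treatment.** Take the 60 kg man with an assumed creatinine of 1.0 mg/dL at Cycle 1. His 3.1(k) clearance is 75 × 60 / 72 = 62.5 mL/min, so 10 mg is correct. If creatinine rises to 1.1 mg/dL before Cycle 3, 3.1(k) gives 56.8 mL/min and the 5 mg row. Item 4c gives 66.8 mL/min and leaves him on 10 mg.

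**The case against.** The strongest reply is that Section 4.0, not Section 5.0, assigns the dose, and the note under its table points to Section 3.1. On that reading all three branches apply by reference, and Section 5.0 is only an abbreviated list of tests. A site that follows the reference would use actual weight and choose 5 mg. This stands in part: the protocol does not uniformly instruct overdosing. But the note itself names ideal body weight, the weight that 3.1(k) does not use below ideal, and Section 5.0 does not refer to the note. Two careful readers could therefore reach different doses.

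A second reply concerns the route to the wrong dose. Item 3c applies only when baseline tests are more than 7 days old. Otherwise the 3.1(k) value governs Cycle 1, and a later error would mean raising a patient from 5 to 10 mg, which no text describes. Section 7.0 speaks only of reductions within a patient. This narrows the route without closing it. The Section 4.0 table sets the dose by clearance for each lenalidomide cycle, item 3c can apply at Cycle 1, and, as in Step 5, a patient already on 10 mg whose clearance falls would wrongly stay there with no increase needed.

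Third, the group is small and the harm bounded. A patient must be below ideal weight and within about 3 to 12 mL/min under the cut (95% to 80% of ideal), in a trial of 40. The 10 mg dose is the protocol's starting and highest dose, and the Day 14 blood count and the hold and reduction rules remain in force. All of this is right, and it limits the weight of the point. Those safeguards act after exposure, however, and none rechecks the weight used.

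**Conclusion.** The concern holds. Items 3c and 4c of Section 5.0 conflict with Section 3.1(k) for every patient below ideal weight, and the Section 4.0 note does not resolve the conflict. The omission and its direction are certain from the text and the form of the equation. The consequence, 10 mg instead of 5 mg daily, arises when the 3.1(k) clearance is above 60 × (actual/ideal) and at most 60 mL/min, and when staff apply Section 5.0 as written.

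How many of the 40 expected patients would fall in that window is unknown and could be none, because the documents give no weight or renal distribution. Eligibility rests on 3.1(k) alone and is unaffected. No effect on the toxicity rate, the stopping boundaries or any planned analysis is claimed. The point should be corrected because it affects dosing in a safety study, but it does not threaten the design.

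**What to change.** In Section 5.0, items 3c and 4c, and in the note under the Section 4.0 dose table, replace the weight wording with *creatinine clearance calculated as defined in Section 3.1(k)*. The three-branch rule, including actual weight at or below ideal, then governs every lenalidomide dose assignment, at the starting level and at the fallback level.

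The cost is one phrase in three places. Sample size, stopping boundaries, visits and tests do not change.

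### Myeloma response criteria: the calcium and 5% marrow limits conflict as printed, and so does the VGPR urine limit if the source file really says 4h

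*Combined protocol and SAP*

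**What the plan says.** Section 5.0 (Evaluation During Study), item 9, adopts the IMWG uniform criteria for myeloma patients and then prints the thresholds.

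- **Progressive disease, calcium:** hypercalcemia counts when it is due to the myeloma alone, with the limit written as "corrected serum calcium > 11.5 mg/dL or 2.65 mol/L". Hypercalcemia is also listed, without a limit of its own, as a sign of relapse from CR.
- **Marrow:** CR requires no more than 5% "plasma cells in the bone marrow". Relapse from CR is met when 5% or more develops, and any one relapse criterion is enough.
- **Urine M protein:** the heading "Very good partial response (VGPR) (one of the following" means that either route suffices. The second route is "90% or greater reduction in serum M protein plus urine M protein level < 100 mg per 4h". The next category down is headed "Partial response (PR) (all of the following". It needs a serum fall above 50% and, for urine, "Reduction of urinary monoclonal protein to < 200 mg/24h" or a fall above 90%.

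Overall response rate and progression-free survival are secondary objectives (sections 1.0 and 7.0). Section 9.2 makes disease progression a criterion for removal from the study. Multiple myeloma is a named eligible disease for autologous patients (section 3.1c).

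**The concern.** These lines decide whether a patient is a responder and when a patient has progressed. If two printed limits disagree, two assessors can follow the protocol and classify the same patient differently. Ordered categories should also nest: a patient who meets VGPR should meet every PR condition. As printed, the urine limit breaks that order. No other section says which value prevails. Naming the IMWG criteria does not settle it, because the protocol prints its own numbers under that name.

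**Working it through.** **1. Calcium.** Inputs: 11.5 mg/dL and 2.65 mol/L (section 5.0, progressive disease). The atomic mass of calcium, 40.078 g/mol, is a physical constant not given in the documents. Formula: mmol/L = mg/dL × 10 / 40.078.

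- 11.5 × 10 / 40.078 = 2.87 mmol/L, so the protocol's pair of figures does not reproduce.
- Reading mol/L as mmol/L: 2.65 × 40.078 / 10 = 10.6 mg/dL. The two limits differ by 11.5 − 10.6 = 0.9 mg/dL.
- Reading mol/L literally: 2,650 × 40.078 / 10 ≈ 10,600 mg/dL, which is impossible.
- A corrected calcium of 11.0 mg/dL, due to myeloma alone, is above one limit and below the other.

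**2. Marrow.** CR covers values ≤5% and relapse from CR covers values ≥5%. The two ranges share one value, exactly 5%. A CR patient who goes from 2% to 5% still meets the CR marrow limit and has also met a relapse criterion.

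**3. Urine, if 4h is what the source file says.** Scaling by time at a constant excretion rate: 100 mg/4h × 6 = 600 mg/24h, and 600 / 200 = 3 times the PR limit.

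| Patient: serum down 90%, urine 1000 to 400 mg/24h | Serum | Urine | Result |
|---|---|---|---|
| VGPR, second route | ≥90%: met | 400 < 600: met | VGPR |
| PR | >50%: met | 400 is not < 200; fall is 600/1000 = 60%, not >90% | Not PR |

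In general, a patient meets VGPR and fails PR when the serum fall is at least 90%, urine is at least 200 and below 600 mg/24h, and the urine fall is 90% or less.

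If the limit were 100 mg/24h, the conflict would vanish: below 100 implies below 200, and a serum fall of at least 90% implies more than 50%. The patient in the table would then meet neither category and, absent progression, would be stable disease.

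**4. Scale.** One reclassified patient moves an arm's response rate by 1/25 = 4.0 points (autologous) or 1/15 = 6.7 points (allogeneic). For comparison, section 7.0's intervals at a 20% response rate reproduce:

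- n = 25: 0.20 ± 1.96 × √(0.2 × 0.8 / 25) = 0.20 ± 0.157, giving (0.043, 0.357).
- n = 15: 0.20 ± 1.96 × √(0.2 × 0.8 / 15) = 0.20 ± 0.202, giving (0, 0.402) after truncation at zero.

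A single reclassification is well inside either half-width.

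**The case against.** The strongest reply is that these are transcription slips with little practical effect. Much of it stands.

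- **Urine.** The other timed urine limits in item 9 are per 24 hours, and section 5.0 schedules no 4-hour collection. The text shows digit loss elsewhere: the second entry in section 10.0 has a year cut to one digit. The loss may have arisen only in reading the PDF, in which case the plan has no error here. A reader might also infer that VGPR as a whole is looser than PR. It is not: its serum limit is stricter, and its first route (M protein seen on immunofixation but not electrophoresis) is unaffected. Nor does every patient with urine between 200 and 600 mg/24h depend on the VGPR wording, because a urine fall above 90% satisfies PR.
- **Calcium.** The protocol's other laboratory limits are in conventional units (creatinine and light chains in mg/dL, serum M protein in g/dL), so 11.5 mg/dL would probably be used in practice. The number never decides alone, because the cause must be myeloma only. Even so, the mismatch between the figures does not depend on PDF reading of the unit: with the unit repaired to mmol/L they still disagree.
- **Marrow.** The overlap is a single value, and an unchanged 5% is arguably not a development. After baseline, a myeloma marrow is specified only at the 1-month follow-up and as clinically indicated. A reader might infer that the overlap shifts PFS dates. The documents do not establish this: relapse from CR is listed apart from progressive disease, and the text does not say which of them counts as a PFS event.

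None of this reconciles the printed limits.

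**Conclusion.** The conflict holds as a minor inconsistency in decision thresholds. The calcium figures (0.9 mg/dL apart, with an impossible unit) and the shared 5% boundary hold on the current text. The urine conflict (a factor of 3) holds only if the source file says 4h.

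The effect is confined to myeloma patients, whose number is not stated, and to response rate, PFS and removal for progression. The primary toxicity endpoint and the stopping rules do not use these criteria. The shift of 4.0 or 6.7 points per patient is arithmetic, not a forecast: nothing in the documents shows how many patients, if any, would fall in the affected ranges. Reading the urine point as a switch between responder and non-responder assumes that overall response counts both VGPR and PR, which the text does not spell out. The documents do not show which calcium figure was intended.

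**What to change.** Reconcile the three lines in section 5.0, item 9, with the criteria that the sponsor adopts:

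1. Give one calcium limit in a correct unit. If a second unit is kept, make it the true equivalent.
2. Let only one of the two 5% marrow limits include equality.
3. Check the VGPR urine line in the source file. If it already reads 24h, nothing needs changing there. Otherwise state the limit per 24 hours and confirm that it is no looser than the PR limit.

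The cost is a few words in a protocol correction, with no change to sample size, visits or the safety monitoring. Any myeloma assessments already made near these limits should be read again under the corrected text.

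### As printed, the myeloma PR rule cannot be met without measurable serum M protein, so urine-only and free-light-chain-only patients cannot be scored PR; the direction of the resulting error in the response rate is uncertain.

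*Combined protocol and SAP*

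**What the plan says.** Section 3.1 lists "Multiple myeloma" among the diagnoses that admit autologous patients, and criterion b opens the trial to hematologic and lymphoid malignancies in general. Nothing in section 3 asks for measurable serum M protein.

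Section 5.0, item 9, adopts a named standard: "We will use the International Myeloma Working Group (IMWG) uniform response criteria for multiple myeloma patients". It then prints the categories in full.

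- **PR** is headed "Partial response (PR) (all of the following". Its first item is a fall of more than 50% "in serum monoclonal protein". Its second begins "Reduction of urinary monoclonal protein to" and is met below 200 mg/24h or by a fall of more than 90%. Neither item is limited to patients in whom that protein is measurable, and no FLC item follows.
- **VGPR** needs one of two items: M protein seen on immunofixation but not on electrophoresis, or a 90% fall in serum M protein with a low urine level.
- **CR** needs negative immunofixation together with marrow and plasmacytoma conditions. It has no FLC condition; among the response categories only sCR uses FLC, through a normal ratio.
- **PD** needs any one of several items. They include a rise in the urine M component and a rise of at least 25% in the difference between involved and uninvolved "FLC levels (absolute increase must be > 10 mg/dL". Printed just before the FLC item is the note "Only in patients without measurable serum and urine M protein levels".
- **Stable disease** is whatever is left over.

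FLC is assayed at baseline (item 2d) and after treatment (item 7h): "Serum free kappa and lambda light chain assay at each visit". Section 7.0 estimates response at the end of eight cycles and overall, with a 95% confidence interval.

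**The concern.** The progression list recognises patients who can be followed only by urine M protein or only by FLC. The PR list does not. Because both PR items are mandatory and the first is a serum item, a patient with no measurable serum protein cannot be scored PR, even after a large fall in the marker by which the disease is followed. Unless CR or VGPR is met, that patient is scored as stable.

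Overall response rate is the first secondary objective, and section 7.0 intends the response data to inform later studies. The arms are small (25 autologous, 15 allogeneic), so a single misclassified patient is visible in the estimate. The confidence interval describes sampling error and does not cover a scoring rule that fails for one type of patient.

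**Working it through.** **The plan's own figure.** The only figures given for this endpoint are asymptotic intervals at a 20% response rate, p ± 1.96 × √(p(1 − p)/n).

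- n = 25: 0.20 ± 1.96 × √(0.16/25) = 0.20 ± 0.157, giving (0.043, 0.357), as stated.
- n = 15: 0.20 ± 1.96 × √(0.16/15) = 0.20 ± 0.202, giving (−0.002, 0.402), stated as (0, 0.402).

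Both reproduce. They are not in dispute and serve as a yardstick below.

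**Literal scoring of three patients** (illustrative falls, printed rules):

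| Marker at baseline | Change | PR serum item | PR urine item | PR? | Route to PD |
|---|---|---|---|---|---|
| Serum M protein | serum −60%, urine item met | met | met | yes | serum M protein |
| Urine M protein only | urine −95% | cannot be met | met | no | urine M component |
| FLC only | FLC difference −80% | cannot be met | taken as met | no | FLC difference |

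The position of the note before the FLC item leaves its scope slightly unclear: it may introduce the FLC item or qualify the urine item. On either reading both light-chain groups keep a route to PD, and the PR result does not change.

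**What remains open above PR.**

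- VGPR item 2 needs a serum fall, so it is closed to both light-chain groups.
- VGPR item 1 needs no serum fall. Some patients with urine M protein can reach it when the protein is no longer seen on electrophoresis.
- The plan does not define measurable. If it means visible on electrophoresis, a patient with neither protein measurable but positive immunofixation already satisfies VGPR item 1 at baseline. One with negative immunofixation already satisfies the immunofixation part of CR, leaving only the marrow and plasmacytoma conditions. Neither needs any fall in FLC.

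The printed rules can therefore err both ways: a real partial response scored as stable, or an unchanged FLC-only patient scored as VGPR or CR.

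**Effect per patient.** One patient is 1/25 = 4 points in the autologous arm and 1/15 = 6.7 points in the allogeneic arm. Starting from a 20% rate (5 of 25, or 3 of 15):

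| Error | N = 25 | N = 15 |
|---|---|---|
| 2 responders missed | 3/25 = 12% (0, 0.247) | 1/15 = 6.7% (0, 0.193) |
| 1 responder missed | 4/25 = 16% (0.016, 0.304) | 2/15 = 13.3% (0, 0.305) |
| none | 5/25 = 20% (0.043, 0.357) | 3/15 = 20% (0, 0.402) |
| 1 non-responder credited | 6/25 = 24% (0.073, 0.407) | 4/15 = 26.7% (0.043, 0.490) |

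**How many patients?** The documents give no count. Assume 10 of 25 autologous patients have myeloma, 10% to 30% of those lack measurable serum M protein, and 20% (the plan's illustrative rate) to 40% of these have a true partial response. Missed PRs are then 10 × 0.10 × 0.20 = 0.2 to 10 × 0.30 × 0.40 = 1.2 patients, or 0.2/25 = 0.8 to 1.2/25 = 4.8 points. Every input except the 20% and the 25 is assumed. The range covers missed PRs only, before any VGPR credit or over-crediting.

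**The case against.** Four arguments can be made on the other side.

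1. **The plan names the IMWG criteria, so assessors may apply the full source wording.** That is possible, and the source was not available for this review. But the plan prints its own list under that name, and the printed list is what it specifies. If one assessor used the list and another the source, the same patient could be scored in two ways.
2. **Light-chain patients are not shut out of response.** This stands. A reader might infer that the scale can record no improvement short of CR for these patients. The documents do not support that, because VGPR needs only one item and its first item asks for no serum fall.
3. **The direction is not known.** This also stands. A reader might infer that the response rate is biased downwards. It may not be: neither CR nor VGPR item 1 carries an FLC condition, so an FLC-only patient could be credited without any FLC response.
4. **Little turns on it.** The primary objective is safety, all stopping rules concern toxicity, and response is estimated with no test or decision threshold. The assumed shift of 0.8 to 4.8 points is well inside a half-width of about 16 points at N = 25. This limits the weight of the point. It does not remove it, since a few words would make the endpoint scoreable for these patients.

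**Conclusion.** The point holds for PR, and it is a fault in the printed rule rather than a missing detail. Without measurable serum M protein, PR is unreachable, while PD can still be called on the urine component or the FLC difference. This applies to urine-only patients as well as to those followed only by FLC.

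The net direction of error in the response rate is uncertain, because missed partial responses and over-credited CR or VGPR work against each other. The size is 4 points per misclassified patient at N = 25 and 6.7 points at N = 15, times a number of patients that the plan does not give and that may be zero. The conclusion rests on the printed list being used as written and on at least one such patient enrolling, which the eligibility criteria allow. It is a minor-to-moderate correction to a descriptive secondary endpoint and does not touch the safety objective.

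**What to change.** Amend the criteria in section 5.0, item 9:

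- State what counts as measurable serum and urine M protein at baseline.
- Apply the PR serum item only when serum M protein is measurable at baseline, and the PR urine item only when urine M protein is measurable at baseline.
- When neither is measurable, score PR on a fall of at least 50% in the involved-minus-uninvolved FLC difference, and VGPR on a fall of at least 90%. These mirror the 50% and 90% levels that the plan already uses for serum M protein.
- Do not credit these patients with CR or VGPR on immunofixation or electrophoresis alone.

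An FLC route by itself would not be enough, because urine-only patients would still be held back by the mandatory serum item. If the sponsor prefers not to add routes, the minimum is to declare such patients not evaluable for PR and to say how the denominator treats them.

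The cost is one or two lines of text beyond the definition of measurable. Serum and urine electrophoresis, immunofixation and the FLC assay are already collected at baseline and at each follow-up visit, so no new test or visit is needed.
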